### **STATISTICAL CONSIDERATIONS:**

Primary goal of this study is to assess the benefit of zinc supplementation by increasing zinc levels and hence improving several important biomarkers. To assess the effect of supplementation and its' positive influence on markers of inflammation and immune activation known to be associated with HIV-comorbidities, 95 HIV+ subjects (see below for the sample

size justification) will be studied for 6 months from the available HIV+ subjects pool. During this period outcome variables (primarily, zinc levels and sCD14) and biomarkers will be measured at baseline (0), 6, 12, 18, and 24 weeks. The outcome variables will be analyzed, and predicted values will be portrayed longitudinally. The main outcome variables zinc levels and sCD14 are continuous variables. Therefore, linear mixed model and likelihood ratio test will be used in testing hypotheses (see details below).

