The HIV+ subjects in the supplementation arm will take 90 mg elemental zinc daily for 24 weeks whereas the HIV+ subjects in control arm will take matching placebo. Both groups of subjects will be in the study for 24 weeks. Outcomes of the intervention will be measured longitudinally at baseline (0), 6, 12, 18 and 24 weeks as noted in the Schedule of Evaluations Table. These outcome variables are in continuous scale. Linear mixed-effects modeling will be used in analyzing these longitudinal measurements to understand their trajectories over the study period. We will collect information on the covariates demographics, lifestyle habits, dietary and socioeconomic factors, and HIV/ART factors. For reproducibility of the results, the data quality will be reviewed rigorously, and necessary transformations will be performed to satisfy assumptions related to residuals for parametric models. Basic descriptive statistics will be used to summarize outcomes and covariates within each group of subjects. We anticipate that the two groups will show some but not complete overlap in their distributions in terms of our baseline covariates. To depict the impact of supplementation, summary statistics as well as predicted values of longitudinally measured outcome variables will be presented graphically. Models for longitudinally measured outcome variables, analysis method, and computation of power are presented below. One-sided hypothesis tests are performed assuming a 0.10 level of significance (standard for phase II trial). The error rate in multiple comparisons will be controlled by the step-up Bonferroni correction procedure. The sample size estimation will be based to achieve power of 0.80.

**Aim 1&2:** we assess the benefit of the zinc supplementation in HIV+ patients. In these aims we will study the impact of zinc supplementation in increasing zinc levels and improving markers related to HIV-comorbidities. We will measure the outcome variables in two-groups at 5 times points during 6 months period. To delineate the outcomes over 6 months period, we will analyze the 6 months outcome data using a linear mixed-effects model. Let  $Y_{ij}$  denote an outcome variable from the  $i$ th subject at the  $j$ th week, where  $i=1, 2, \dots, 95$  HIV+ subjects;  $j=0, 6, \dots, 24$  weeks. Define  $T_{ij}$  to be the week when the response measurements are collected from subject  $i$ . A linear mixed model for the outcome  $Y_{ij}$  can be written as

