
$$Y_{ij} = \alpha + \beta_0^T X + \beta_1 I + \beta_2 T_{ij} + \beta_3 I \times T_{ij} + \nu_{0i} + \nu_{1i} T_{ij} + \varepsilon_{ij} \quad (1),$$

where  $X$ =vector of covariates,  $I$ =zinc supplementation (yes/no), the vectors of random effects  $\nu_i = (\nu_{0i}, \nu_{1i})'$  are assumed to be independent multivariate normal with mean vector 0 and covariance matrix  $G(\theta) = G(\sigma_{v11}, \sigma_{v12}, \sigma_{v22})$ . The error term  $\varepsilon_{ij}$  in model (1) is assumed to be distributed as normal  $(0, \sigma^2)$ . The  $\beta$ 's are fixed effects parameters, and  $G$  is assumed to be an unstructured covariance matrix. From the fitted model (1), we will delineate the predicted outcome variables, association between outcomes and zinc supplementation therapy. The model parameters will be estimated by the method of restricted maximum likelihood. Likelihood ratio tests will be used to compare overall mean curves for the two-group. Tests for inequality in 2-group at baseline (0), 6, 12, 18, and 24 weeks will be performed with multiple testing corrections using the Bonferroni correction procedure. Note that if there are large numbers of missing values in this longitudinal study, we will estimate the parameters by utilizing the "pattern

mixture model" which assumes model (1). In the case of parametric model assumption violation, we will consider using the generalized estimating equation approach; but this will be avoided, if possible, because it will lead to decreased power.

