**Sample Size and Power analysis:** The following sample size estimation and power analysis is based on the significance level 0.10 and 80% power. We hypothesize that after the zinc supplementation the HIV+ subjects will have higher levels of zinc and lower levels of sCD14. Based on our data from SATURN-HIV study, we assume that, at baseline/before the supplementation, the average  $\pm$  SD of log(sCD14) for all HIV+ subjects is  $7.66 \pm 0.32$ . Using Frison and Pocock's change method, we estimate the sample size based on the difference in the two groups of the mean change of the post-intervention measurements at month six from the baseline measurement, assuming that correlation between repeated measurements is 0.85. A mean difference of 0.08 ng/ml log(sCD14) change between two groups, 27 HIV+ subjects in the control arm and 54 HIV+ subjects in the intervention arm, in a longitudinal measures design with 5 longitudinal measurements can be detected with 80% power using a t-test. In this prospective longitudinal study we anticipate 15% subjects missing/non-compliance because of variety of reasons. Therefore, our final sample size estimates for the control and intervention arms are 31 and 62, respectively. The sample size estimation was performed using STATA 14.0.

**Effect size consideration:** As above, we previously stated that we will perform significance tests for the shift of distributions of biomarkers after the zinc supplementation using Kolmogorov-Smirnov (K-S) test. The amount of shift or effect size will be measured using Cohen's d value. For estimating the effect size, we used our statin study data as the preliminary

data (NCT01218802). In the statin study the baseline mean (SD) of hs-CRP, log(sCD14), log(sTNF-RI), and LBP are 4.95(10.45), 7.71 (0.35), 7.46 (0.37), and 21.11(10.91), respectively. For zinc supplementation (90 mg) we will compute the change in a biomarker by taking the difference of a biomarker measured before- and after- the zinc supplementation. For example, we will compute the difference in LBP measured at baseline and after the zinc supplementation. Similarly, differences will be computed for the other biomarkers. The effect size estimation is performed using nQuary Advisor 7.0 software.

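### The plan fits the mixed model by restricted maximum likelihood (REML) and compares the arms' mean curves by likelihood ratio tests with no maximum likelihood refit stated; as written, the statistic is not chi-square and depends on numerical scale

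*Combined protocol and SAP*

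**What the plan says.** The opening of Statistical Considerations names zinc and sCD14 as the main outcomes and says that a "linear mixed model and likelihood ratio test will be used in testing hypotheses".

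Under Aim 1&2, model (1) has an arm term (β1), a time term (β2), an arm-by-time term (β3), covariates, and a random intercept and slope. The β's are declared fixed effects, and time is defined "to be the week when the response measurements are collected from subject". Two consecutive sentences then give the estimator and the test: the parameters are "estimated by the method of restricted maximum likelihood. Likelihood ratio tests will be used to compare overall mean curves for the two-group". The level is 0.10 ("One-sided hypothesis tests are performed assuming a 0.10 level of significance").

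The section does not say that the models being compared will be refitted by ML, and it offers no Wald or F test of the arm terms. It does plan separate between-arm tests at each visit with a Bonferroni correction. The sample size paragraph is based on a t-test.

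**The concern.** In model (1) the two mean curves differ only through β1 and β3. Comparing them by a likelihood ratio test means comparing a model with these two terms against one without them, that is, two models with different fixed-effect designs. REML estimates variance components from contrasts of the data that are free of the fixed effects. Change the fixed effects and the contrasts change, so the two restricted likelihoods describe different data. Twice their difference has no chi-square reference, and it moves with choices that should not matter, such as the unit of an outcome.

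This is the test that the plan assigns to its main outcomes. Followed literally, it would give p-values without meaning. Because the markers sit on very different numerical scales, it would also hold different endpoints to different effective thresholds.

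**Working it through.** **Inputs.** From the sample size paragraph: log(sCD14) mean 7.66, SD 0.32; correlation 0.85; effect 0.08; 27 control and 54 zinc evaluable, 31 and 62 planned; level 0.10. Assumed, because the plan does not give them: natural log, effect shape (linear to week 24, or constant after baseline), random-slope SD of 0 to 0.10 per 24 weeks, no covariates, no missing data.

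**The plan's own figure.** The change method has variance SD² × [(1+(r−1)ρ)/r + 1 − 2ρ]. With r = 5 post-baseline values this is 0.1024 × (0.88 + 1 − 1.70) = 0.018432. At two-sided 0.10, control n = 1.5 × 0.018432 × (1.645 + 0.842)² / 0.08² = 26.7, so 27 and 54 are reproduced. With r = 4 it gives 28 and 56. The inputs are therefore read correctly. The 80% power belongs to a t-test, not to the likelihood ratio test.

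**Why the statistic fails.** In its usual form, for N observations and p fixed effects,

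−2 log L(REML) = (N−p) ln(2π) + ln det V + ln det(X'V⁻¹X) + r'V⁻¹r.

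The first and third terms depend on the fixed-effect design. They do not cancel when β1 and β3 are dropped (p falls by 2).

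- Outcome multiplied by k: −2 log L rises by 2(N−p) ln k. The reduced model has two fewer fixed effects, so the difference moves by 2 × 2 × ln k = 4 ln k. For zinc in µg/dL (Rationale) instead of mg/L (Inclusion Criteria), k = 100 and the shift is 4 × 4.605 = 18.4.
- Time divided by c: the full model has two time columns and the reduced model one, so the difference moves by 2 ln c. Weeks to months gives 2 ln(4.345) = 2.94.

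The 0.10 critical value on 2 df is 4.61. An ML likelihood ratio statistic does not move under either change.

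**Simulation of model (1), 2-df test, compound symmetry, time in weeks** (1,000 runs per row at 27/54, 300 at 31/62):

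| Control/zinc, visits | True effect | REML mean | REML rejects | REML rejects, outcome ×100 | ML mean | ML rejects |
|---|---|---|---|---|---|---|
| 27/54, five | none | −12.64 | 0.0% | 68.4% | 1.95 | 10.2% |
| 27/54, five | 0.08 linear | −7.93 | 1.6% | 96.2% | 6.70 | 62.4% |
| 27/54, five | 0.08 constant | −9.01 | 0.5% | 93.4% | 5.60 | 51.9% |
| 31/62, five | none | −12.69 | 0.0% | 65.3% | 2.17 | 11.7% |
| 31/62, five | 0.08 linear | −7.70 | 2.3% | 95.3% | 7.19 | 66.7% |
| 31/62, five | 0.08 constant | −8.98 | 1.3% | 90.3% | 5.89 | 53.0% |
| 31/62, three (0, 12, 24) | none | −12.38 | 0.0% | 76.0% | 2.24 | 12.7% |
| 31/62, three (0, 12, 24) | 0.08 linear | −8.46 | 2.0% | 92.7% | 6.20 | 57.0% |

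The three-visit rows follow the schedule of evaluations, which shows the markers only at entry and weeks 12 and 24.

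**Other settings.**

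- Testing the interaction alone (1 df), REML rejects in 1.0 to 5.3% at the planned effect and in 0 to 0.3% with none.
- With a random-slope SD of 0.10, 31/62 and three visits (100 runs per setting), the 2-df REML statistic averages about −8.8 in weeks and −6.1 in months and rejects in about 1%. With the outcome ×100 it rejects in 95% with the effect and 79% without. ML averages about 5.5 and rejects in about 50%.
- With slope SD 0, a separate run at 31/62 gives ML power of 60% (three visits) and 68% (five visits).

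**A further dependence.** Some forms of the restricted likelihood subtract ln det(X'X). At 27/54 with five weekly-coded visits, each subject's design has determinant 5 × 1080 − 60² = 1800. The added shift is ln[(27 × 54/81)² × 1800] = ln(583,200) = 13.28. That moves the no-effect mean from −12.64 to 0.64 and removes the dependence on time units. The 4 ln(k) shift stays: with the outcome ×100 the no-effect mean would be 0.64 + 18.42 = 19.06.

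**The case against.** The strongest reply is that the plan omits a detail rather than making an error. The estimator and the test stand in separate sentences, and neither says that restricted likelihoods are the ones compared. Using REML for estimates and ML for the test is compatible with the wording and may be what the statistician intends. That is fair, but the only fitting method named is REML, and the test follows in the next sentence. A programmer working from the text has no instruction to refit.

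Three stronger readings are tempting, and the documents do not support them.

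- **That the test would simply miss a true effect.** This holds for natural-log sCD14 with time in weeks, in the form of likelihood shown. On a numerically large scale the same test rejects mostly when nothing is there. For zinc the plan gives neither an SD nor a planned effect, so no rejection rate can be computed.
- **That the p-value for sCD14 is set by its measurement unit.** On a log scale, changing the concentration unit only moves the intercept, and the plan fixes time in weeks. The unit argument applies to outcomes analysed unlogged. It would not apply to zinc if zinc were logged, which the plan's allowance for transformations permits. The µg/dL figure is also in rationale text, not in the analysis specification.
- **That no valid comparison of the arms would remain.** Per-visit tests are also planned. They do not replace the test that the plan names for its main outcomes.

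It is also true that a statistic that is negative in more than 90% of trials would probably alert an analyst. That is no reason to leave the text as it is, since on other scales the statistic would look plausible.

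**Conclusion.** Wrong as written. That the statistic is not chi-square, and that it shifts by 4 ln(k) with the scale of an unlogged outcome, is algebra and needs no trial assumption.

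The size for sCD14 is conditional. With natural log, weeks, SD 0.32, correlation 0.85 and slope SD 0 to 0.10, the 2-df test rejects in 0.5 to 2.3% of trials at the planned effect, and testing the interaction alone extends this to about 5%. With no effect it rejects in about 0%. The 2-df ML version has about 50 to 68% power. With the outcome ×100, false rejection is about 65 to 80%. These rates also assume the usual form of the restricted likelihood; software that adds the design-matrix term would give others, which is itself a sign that the quantity is not a test statistic.

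The direction of error is therefore not fixed. If an ML refit is what the statistician intends, the defect lies in the text alone, but the text still has to say so.

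**What to change.** In the paragraph below model (1), state that any likelihood ratio test of the arm and arm-by-time terms compares two nested models both fitted by maximum likelihood. Alternatively, keep REML and test these terms with a Wald t or F test with Kenward-Roger degrees of freedom. Either way, keep REML for the reported estimates and for comparing covariance structures. Make the sentence in the section's opening paragraph agree with the choice.

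The cost is one sentence of wording. It needs no extra data, visits or participants.

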**Correlational analyses of the secondary and exploratory objectives:** To assess the associations of concurrently measured biomarkers, we will present descriptive statistics at each time point, plot the individual/group trajectory of changes, and apply bivariate linear mixed effects models ([14]). Here we use biomarker as a general term to indicate that it is a continuous variable from a statistical point of view. We will compute summary statistics (mean, median, SD, coefficient of variation, Cohen's d, etc.) for each biomarker, at each time point. We will plot these summary statistics over the study period for better understanding the trajectory of these biomarkers. Specifically, we will be presenting two biomarker summary statistics in each graph for better understanding the trajectory of one biomarker and its relationship with the other relevant biomarker: HOMA-IR vs. Zinc. We expect that an increasing trend in zinc should lead to a decreasing trend in HOMA-IR level. We will also plot the biomarkers at each time point using box plots. The box plots will depict a biomarker distribution at every time point (baseline, week 12 and 24). The box plots will give us an overall direction of change in the study population. Since our focus is in the treated group, we will present biomarker trajectories using spaghetti plots for examining individual changes. The spaghetti plots will help in determining analysis models. We will apply the bivariate linear mixed effects (BLME) model for studying evolving relationship in two biomarkers. The BLME model is an extension of equation (1), which allows jointly analyzing two biomarkers together. The BLME model will include random effects and/or first-order auto-regressive process, and independent measurement error for both biomarkers. The joint analyses will provide estimates of correlation coefficients among the biomarkers[14]. Again, for the correlational analysis our focus will be the treated group. The BLME model for Gaussian longitudinal biomarker data will be implemented in SAS MIXED procedure. For faster computational benefit, we will apply the Newton-Raphson algorithm, instead of EM algorithm.

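### The likelihood-ratio test named for zinc and sCD14 reads as an undirected 2-df test; it matches neither the one-sided 0.10 rule nor the t-test for which the trial was powered

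*Combined protocol and SAP*

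**What the plan says.** All references are to Statistical Considerations in the combined protocol and SAP unless stated.

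- **Test.** The opening paragraph says of zinc and sCD14 that a "linear mixed model and likelihood ratio test will be used in testing hypotheses". Under Aim 1&2, after model (1), it adds: "Likelihood ratio tests will be used to compare overall mean curves for the two-group". Model (1) contains an arm term (beta1), a linear week term (beta2) and an arm-by-week term (beta3). No null hypothesis in terms of the betas and no df are given.
- **Per-visit tests.** The next sentence plans Bonferroni-corrected tests of inequality between arms at weeks 0, 6, 12, 18 and 24.
- **Sidedness.** "One-sided hypothesis tests are performed assuming a 0.10 level of significance".
- **Direction.** The sample size section expects that after supplementation "subjects will have higher levels of zinc and lower levels of sCD14".
- **Power.** That section says the "power analysis is based on the significance level 0.10" and does not repeat sidedness. The 0.08 difference in log(sCD14) change, with 27 controls and 54 on zinc, "in a longitudinal measures design with 5 longitudinal measurements can be detected with 80% power using a t-test".
- **Visits.** Aim 1&2 says "We will measure the outcome variables in two-groups at 5 times points during 6 months period". The schedule tables mark inflammation markers at entry, week 12 and week 24 only. The correlational analyses agree with the tables, describing the biomarker "distribution at every time point (baseline, week 12 and 24").

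**The concern.** Three statements should describe one test and do not. The named test compares whole mean curves. The decision rule is one-sided. The powered test is a t-test on change from baseline.

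Under model (1), equal mean curves means beta1 = beta3 = 0. A joint test of two parameters has no sign: it rejects as often for a 0.08 rise in log(sCD14) as for a 0.08 fall, so rejection alone does not support the stated hypothesis. One of the two df goes to beta1, the week-0 gap between arms, which randomization already makes zero on average. If this test decides the main outcomes, a true effect of the planned size is missed more often than the one in five that the reader of the sample size section would expect.

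**Working it through.** **Inputs.** From the sample size section: SD 0.32, correlation 0.85, 27 controls and 54 on zinc (1/27 + 1/54 = 1/18), difference 0.08, level 0.10. Visits are weeks 0/12/24 (schedule tables) or 0/6/12/18/24 (Aim 1&2). Equal correlation between all visits, no gain from covariates and no loss beyond 27/54 are assumed.

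**1. Reproduce 27/54.** With one baseline and the mean of p later values, the change method at 2:1 allocation gives

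controls = 1.5 × 0.32² × k × (z + 0.842)² / 0.08² = 24 × k × (z + 0.842)², with k = [1 + (p − 1) × 0.85]/p + 1 − 2 × 0.85.

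| Later values p | k | Two-sided 0.10 (z = 1.645) | One-sided 0.10 (z = 1.282) |
|---|---|---|---|
| 5 | 0.18 | 26.7, so 27/54 | 19.5, so 20/40 |
| 4 | 0.1875 | 27.8, so 28/56 | 20.3, so 21/42 |
| 1 (month six only) | 0.30 | 44.5, so 45/90 | 32.5, so 33/66 |

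The plan's figure reproduces exactly only as a two-sided 0.10 calculation with five later values. Five visits including baseline leave four. At 27/54, the month-six-only t-test has 74% power one-sided and 62% two-sided.

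**2. Power of the 2-df test.** The vector of arm differences over visits has covariance W = 0.32² × (0.15 I + 0.85 J)/18. With Z = [1, t] and b the generalized least squares estimate, the noncentrality is b′(Z′W⁻¹Z)b, compared with chi-square on 2 df (critical value 4.605).

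| Effect on log(sCD14) | Weeks 0/12/24 | Five visits |
|---|---|---|
| Linear, 0.08 at week 24 | 4.063: 55% | 5.007: 63% |
| 0.08 from the first post-baseline marker visit | 4.306: 57% | 3.818: 53% |
| Linear, averaging 0.08 over post-baseline visits | 7.22: 78% | 12.82: 95% |

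In the last row the week-24 effect is 0.08/0.75 = 0.107 or 0.08/0.625 = 0.128, so the noncentralities are 4.063/0.75² and 5.007/0.625². Simulated likelihood-ratio tests with ML fits at five visits (1,000 trials each) gave 60% for the linear effect and 53% for the sustained one, with 11% rejection under the null.

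Power of 80% on 2 df needs noncentrality 7.71. For the first row that is 27 × 7.71/4.063 = 51.2, so 52 controls, or 27 × 7.71/5.007 = 41.6, so 42 controls.

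**3. Directional 1-df tests, one-sided 0.10, 27/54.**

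- *beta3, linear effect.* Scaled to 24 weeks, SE = 0.32 × √(0.15/(18 S)), where S is the sum of squares of t: 0.5 for three visits, 0.625 for five. SE is 0.0413 or 0.0370, z = 1.936 or 2.165, and power is 74% or 81%.
- *beta3, effect present from the first post-baseline visit.* With three visits z is unchanged (74%). With five, the fitted 24-week slope is 0.064, z = 1.732, and power is 67%.
- *Week-24 contrast, categorical time, common baseline mean.* SE = 0.32 × √(1 − 0.85²) × √(1/18) = 0.0397, z = 2.01, power 77%. Because time is categorical, this depends only on the week-24 difference.
- *Common baseline but linear time kept.* With five visits: 83% for a linear effect, 73% for an early plateau and 67% if the effect appears only at week 24. The shape-free 77% therefore needs categorical time.

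**4. The planned per-visit tests.** A week-24 comparison of levels from model (1), with a linear effect, has z = 1.07 (three visits) or 1.09 (five). Power is about 42% at one-sided 0.10 and about 16–17% at 0.10/5 = 0.02.

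**The case against.** The strongest reply is that the plan contains more than the likelihood-ratio test. The per-visit tests are single-parameter comparisons to which the one-sided rule can apply, and they include week 24. That is fair, but they compare levels rather than change, spend one of five tests on baseline, are Bonferroni-corrected, and none is designated primary. Their power is far below that of a change contrast.

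The 2 df is also an inference. If the sponsor means beta3 alone, a signed 1-df likelihood-ratio test can be one-sided, with about 74–81% power for a linear effect. The reference to overall mean curves points the other way, but a clarifying sentence would settle it.

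Nor is the whole shortfall due to the second df. At two-sided 0.10, beta3 has 62% or 70% power for a linear effect, so the extra df costs about 7 points. The rest of the gap to the one-sided figures (74% or 81%) is sidedness. Any two-sided test rejects in both directions, and the planned plots of predicted values would show which way the effect went.

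Two stronger readings are tempting. A reader might infer that the plan claims 80% power for the likelihood-ratio test and that the claim is false. It does not: the 80% is attributed to a t-test on change. A reader might also infer that sidedness is open for the analyst to settle later. It is not: the section fixes one-sided 0.10, and the sample size paragraph merely fails to repeat it.

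**Conclusion.** The mismatch is real and should be fixed. The test named for the main outcomes, read naturally, is undirected on 2 df, while the decision rule is one-sided and the powered test is a t-test on change. For log(sCD14) at 27/54 with 0.08 reached at week 24, the 2-df test has about 55% or 63% power for a linear effect and 57% or 53% for an immediate sustained one. It comes near or above 80% only if 0.08 is the average of a linear effect over the post-baseline visits, which is not how the sample size section words it: that section speaks of change at month six.

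Separately, 27/54 matches a two-sided 0.10 calculation, not the one-sided rule. These results rest on the inferred 2 df, constant correlation 0.85 and 27/54 evaluable. They concern sCD14 only, since the documents give no power inputs for zinc. This is a failure to align the named test with the powered one. It does not show that the type I error is wrong or that the trial is bound to be judged at 55–63% power.

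**What to change.** In the opening of Statistical Considerations and under Aim 1&2, name one directional 1-df primary test at one-sided 0.10 for each main outcome:

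- **Option one:** the week-24 arm contrast from a mixed model with categorical time and a baseline mean common to both arms. It corresponds to the month-six change in the sample size section and has about 77% power whatever the effect shape. It replaces the linear time term of model (1).
- **Option two:** beta3 in model (1). It keeps the model but has 74% power with three visits. With five visits it has 81% if the effect is linear and 67% if it plateaus early.

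Label any retained likelihood-ratio test of the mean curves supportive, and fit both models by ML, because REML likelihoods are not comparable across different fixed effects. In the sample size section, state sidedness in agreement with the one-sided rule, and restate power for the named test and the visits at which the markers are actually measured.

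The cost is wording and a few lines of SAS, with no new data or visits. The downside is that stated power at 27/54 falls to 74% or 77% with the three scheduled visits. Reaching 80% would need 33 evaluable controls for beta3 (27 × (2.124/1.936)² = 32.5) or 31 for the week-24 contrast (30.02, rounded up), with twice as many on zinc.

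### Corrected between-arm tests are planned at five weeks, but outcomes are assayed at three; the week-0 test is uninformative, weeks 6 and 18 are interpolated, and no single primary contrast is named

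*Combined protocol and SAP*

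**What the plan says.** The Statistical Considerations state that "biomarkers will be measured at baseline (0), 6, 12, 18, and 24 weeks", and repeat that outcomes are "measured longitudinally at baseline (0), 6, 12, 18 and 24 weeks as noted in the Schedule of Evaluations Table". The Sample Size and Power analysis also counts five longitudinal measurements.

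The schedule under Design and Outcomes differs. Zinc is marked at Screen I, entry, week 12 and week 24; inflammation and immune activation markers at entry, week 12 and week 24. The visit procedures agree: weeks 6 and 18 have hematology/chemistries plus samples kept for possible later use, while weeks 12 and 24 have zinc and batch testing of markers. The correlational analysis section also lists only baseline, week 12 and week 24. (The second copy of the schedule, under Study Design, has a broken table in the text available, so I do not rely on it.)

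On testing, the plan says:

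- "linear mixed model and likelihood ratio test will be used in testing hypotheses"
- "Likelihood ratio tests will be used to compare overall mean curves for the two-group"
- "The model parameters will be estimated by the method of restricted maximum likelihood"
- "Tests for inequality in 2-group at baseline (0), 6, 12, 18, and 24 weeks will be performed with multiple testing corrections", using a Bonferroni correction
- "One-sided hypothesis tests are performed assuming a 0.10 level of significance"
- "The error rate in multiple comparisons will be controlled by the step-up Bonferroni correction procedure"

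The sizing uses a t-test on change, and the effect-size paragraph adds a Kolmogorov-Smirnov test. The plan does not say which of these is primary.

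**The concern.** The error rate is divided among five visit tests when only two post-entry visits have outcome data. At week 0 any difference between arms is chance, so testing it uses alpha and cannot show benefit. At weeks 6 and 18 there are no observations, so the tests would use values implied by the straight line fitted through weeks 0, 12 and 24.

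The named tests also differ greatly in power. The visit tests, if made on levels from model (1), leave the baseline difference free and so make little use of the 0.85 correlation on which the trial is sized. The likelihood ratio test has no written null. If it covers both the intercept and the slope difference, it cannot be one-sided. In a study that its design section calls the confirmatory phase, two analysts could follow this text and report different main results.

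**Working it through.** **Inputs (Sample Size and Power analysis).** SD of log(sCD14) 0.32; correlation 0.85; difference 0.08; 54 zinc and 27 placebo evaluable; level 0.10. My assumptions: exchangeable correlation (model (1) also allows random slopes), no gain from covariates, assays at weeks 0, 12 and 24, effect growing linearly to 0.08 at week 24, one outcome, normal approximation.

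**The plan's own figure.** The Frison-Pocock change variance with r post-baseline measurements is SD²[(1+(r−1)ρ)/r + 1 − 2ρ], and control n = 1.5 × variance × (z_α + z_0.80)²/0.08².

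| Sidedness of 0.10 | r | Control / zinc for 80% | Power at 27/54 |
|---|---|---|---|
| two-sided | 5 | 27 / 54 | 80% |
| two-sided | 4 | 28 / 56 | 79% |
| one-sided | 4 | 21 / 41 | 88% |
| one-sided | 2 | 25 / 49 | 83% |

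The stated 27/54 is reproduced exactly only with two-sided 0.10 and five post-baseline measurements. The schedule has two post-baseline assays, and the testing rule is one-sided.

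**Common quantities.** Variance 0.32² = 0.1024. Between-subject part 0.85 × 0.1024 = 0.08704. Within-subject part 0.15 × 0.1024 = 0.01536. Arm factor k = 1/54 + 1/27 = 0.05556. One-sided power = Φ(effect/SE − z_{1−α}).

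**Visit contrasts on levels.** At week t the contrast is β1 + tβ3, with SE² = k × [0.08704 + 0.01536 × (1/3 + (t−12)²/288)].

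| Week | Effect | SE | Power, uncorrected 0.10 |
|---|---|---|---|
| 0 | 0 | 0.0745 | 10% (the error rate) |
| 6 | 0.02 | 0.0723 | 16% |
| 12 | 0.04 | 0.0716 | 23% |
| 18 | 0.06 | 0.0723 | 33% |
| 24 | 0.08 | 0.0745 | 42% |

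All five contrasts are functions of two parameters. At week 24, 0.08/0.0745 = 1.074. At 0.10/5 = 0.02, power is Φ(1.074 − 2.054) = 16%. At 0.10/2 = 0.05, it is Φ(1.074 − 1.645) = 28%. A simulated step-up (Hochberg) rule over the five tests gives 18% instead of 16%. If the effect is complete by week 12, the figures are 24% step-up and 21% plain.

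**Contrasts that use baseline, week 24, uncorrected one-sided 0.10.**

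- Change: SE = √(2 × 0.01536 × k) = 0.0413; power Φ(1.936 − 1.282) = 74%.
- Arm-by-time: Σ(t−12)² = 288, so the SE of 24β3 = √(576/288 × 0.01536 × k) = 0.0413; power 74%.
- Baseline-adjusted: SE = √(0.1024 × (1 − 0.85²) × k) = 0.0397; power 77%.

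**Likelihood ratio test of β1 = β3 = 0.** The noncentrality is 4.06. Against chi-square with 2 df at 0.10, power is 55%.

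**Mean of weeks 12 and 24 minus baseline.** The variance factor is (1.85/2) + 1 − 1.7 = 0.225, so SE = √(0.225 × 0.1024 × k) = 0.0358. With 0.08 at both visits, power is Φ(2.236 − 1.282) = 83%. With 0.04 then 0.08 (mean 0.06), it is Φ(1.677 − 1.282) = 65%.

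**The case against.** Several stronger conclusions are tempting, and the documents do not support them.

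- **Three of the five tests carry no treatment information.** This is true only of week 0. Under model (1) the week-18 contrast has more power (33%) than week 12 (23%). Weeks 6 and 18 are redundant and depend on the straight-line assumption, but they are not empty.
- **The five-way split also cuts the power of change or baseline-adjusted tests.** Such tests cannot be run at week 0, and without assays they cannot be run at weeks 6 or 18. The split applies to level contrasts from model (1), where the matching figures are 16% and 28%.
- **The trial loses its 80% because two measurements are missing.** The sizing method, applied one-sided to the two scheduled post-baseline assays, gives 83% if the full effect is present at both. It falls to 65% if the effect grows linearly.
- **The likelihood ratio test is invalid because estimation is by restricted maximum likelihood.** Restricted likelihoods cannot be compared between models with different fixed effects. However, the plan does not say the statistic would come from those fits, so this needs a clarifying sentence.
- **Direction is absent.** One-sided testing and the expected directions (zinc up, sCD14 down) are stated generally. They are not tied to the likelihood ratio test.

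It is also fair to say that the study title and the monitoring plan call this a pilot, that the level is justified as a phase II standard, and that the visit tests may be meant as follow-up to the likelihood ratio test. Bonferroni under Aim 1&2 may be shorthand for the step-up rule. These points soften the concern. They do not reconcile five measurements with three or supply a primary null.

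**Conclusion.** The point stands. The analysis text and the sizing assume five outcome measurements, and the schedule they cite provides three. The five-visit correction spends alpha on one test that cannot show benefit and on two interpolated ones: 16% power for the week-24 level contrast, against 28% if only weeks 12 and 24 were corrected.

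The choice of contrast matters more than the correction. Even uncorrected, the level contrast has 42%, against 74–77% for week-24 or arm-by-time contrasts that use baseline. The whole-curve likelihood ratio test, on its natural 2-df reading, has about 55% and conflicts with the one-sided rule; its null, its rank among the tests and the family covered by the multiplicity rule need stating.

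Each percentage belongs to the named test for log(sCD14) under the stated assumptions; none is the power of the trial. The plain Bonferroni figures are the worst case. The basis of the stated 80% must be corrected, but lower power does not follow automatically.

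**What to change.** 1. Delete the between-arm tests at weeks 0, 6 and 18. Alternatively, add assays of the stored week-6 and week-18 samples to the schedule.
2. Unless those assays are added, change five measurements to three throughout the Statistical Considerations, including the Sample Size and Power analysis.
3. Name one one-sided 1-df between-arm contrast per co-primary outcome that uses the baseline value, such as the baseline-adjusted week-24 difference or arm-by-time. Label the other tests supportive, and say what the Kolmogorov-Smirnov test compares.
4. If a likelihood ratio test on fixed effects is kept, state its null and degrees of freedom and fit it by maximum likelihood.
5. Use one multiplicity procedure throughout, and say which outcomes and visits it covers.
6. Restate power for the named test, with its sidedness and number of measurements.

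The cost is wording and a new power calculation; the week-12 and week-24 data are already scheduled. Assaying weeks 6 and 18 would add two rounds of assays. Arm-by-time power would then be about 81% under exchangeable correlation, or 76–78% if half to three-quarters of the change variance lies in random slopes. The downside of naming a single-visit or arm-by-time test on the current schedule is that the stated 80% becomes about 74–77% at 54/27, before any correction across outcomes.
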